9.7. Data Analysis

All statistical analyses will be performed by BSRBR using Stata. The annual analyses will include all patients who have received Ruxience (baseline characteristics) and event incidence reports will include all patients with study follow-up data.

Analyses will be undertaken at 12 monthly intervals and will include recruitment details, baseline characteristics and crude event rates.

The final analysis will provide the incidence rates of safety events of interest overall. If sample size allows, additional analysis in subgroups by gender and new users versus switcher from originator will be undertaken.

The general analytic approach will be descriptive and include rates of events of interest among Ruxience-treated patients. Data will be presented as number of events, incidence rates and 95 % confidence intervals. Such analyses will be performed by and at the direction of BSRBR based on an a priori statistical analysis plan (SAP) maintained by University of Manchester and shared with the Sponsor. The codes will be harmonised with other registers conducting similar analysis. A draft set of MedDRA codes is included in:

Index Date

The Index Date is the date of Ruxience initiation. Patients who switch from another therapy to Ruxience while they are enrolled in BSRBR-RA are eligible for enrollment, and the index date will be the date of Ruxience initiation.

Risk Window

Patients will be evaluated for safety events of interest while exposed to Ruxience and accrue person-time from Index Date until the first occurrence of the event of interest, death, date of last scheduled clinical data provision to the register, lost to follow up, exit from the register or completion of 3 years of follow up. The final report will censor all patients at 3 years after Date of Study Start. Follow up will be uniquely determined for each safety endpoint of interest.

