Some outcomes of interest in this study are thought to potentially occur at a higher rate while on the drug, but that increased risk subsides after the drug is discontinued (ie, serious infections, CV events). In these situations, these events will be calculated using a risk window from Ruxience initiation until 270 days (eg, 9 months) after last infusion based on Ruxience's half-life and mechanism of action. This does not apply to patients who were lost to follow-up, have exited the registry, completed 3 years of follow-up or for whom the most recent date of clinical data provision to the register is within the 270 day window, in which case data will be censored on that date instead. Based on The National Institute for Care and Health Excellence (NICE) guidelines on the use of rituximab treatment, most patients will not be considered for further treatment with Ruxience until at least 6 months from the date of last infusion.

For non-melanoma skin cancer (NMSC) and other malignancies, the manifestation of which is expected to be delayed relative to the time of exposure, the outcomes will be evaluated from drug initiation until the first event, loss to follow up or completion of 3 years of follow up, reflecting a once exposed always at risk paradigm.

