CV risk	Major Acute Cardiovascular Events (MACE), combines MI, stroke, and fatal cardiovascular events: I00-I99 as main cause of death, or I20.0, I21, I60-I64 as diagnosis in in- or outpatient care.	See Serious Infections ‘Outcome’ was defined as any first-ever acute coronary syndrome (ACS) event, which in turn was defined as a primary discharge diagnosis of acute myocardial infarction or unstable angina pectoris, or as acute myocardial infarction being the underlying cause of death. For discharge diagnoses, the date of admission to hospital was considered the event date. This outcome definition has	Fatal and non-fatal 10000891 Acute myocardial infarction; 10006147 Brain stem infarction; 10006148 Brain stem ischaemia; 10008034 Cerebellar infarction; 10008088 Cerebral artery embolism; 10008120 Cerebral ischaemia; 10008190 Cerebrovascular accident; 10014498 Embolic stroke; 10019005 Haemorrhagic cerebral infarction; 10019016 Haemorrhagic stroke; 10024033 Lateral medullary syndrome; 10028596 Myocardial infarction; 10028602 Myocardial necrosis; 10033697 Papillary muscle infarction; 10043647 Thrombotic stroke; 10049768 Silent myocardial infarction; 10051078 Lacunar infarction; 10055677 Haemorrhagic

090177e1953dcb50Approved\Approved On: 16-Oct-2020 13:28 (GMT)

Table 2. ICD and MedDRA Codes for Select Safety Endpoints

Event	ARTIS		BIOBADASER, BSRBR, RABBIT
	Operationalisation	Validation ICD	Operationalisation (Final list TBD based on reported endpoints)

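### The 270-day on-drug window does not say whether it runs from each infusion or only the final one; on the latter reading, infection and CV rates are liable to downward bias of unknown size

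*Protocol*

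**What the plan says.** Section 9.7 (Risk Window) begins with a general concept: "Patients will be evaluated for safety events of interest while exposed to Ruxience". Patients "accrue person-time from Index Date until the first occurrence of the event of interest, death" or one of several other censoring dates, and "The final report will censor all patients at 3 years after Date of Study Start".

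For serious infections and CV events the section then sets a narrower window, on the premise "that increased risk subsides after the drug is discontinued". The rule is "these events will be calculated using a risk window from Ruxience initiation until 270 days (eg, 9 months) after last infusion", justified by half-life and mechanism of action. It has one start (initiation) and one end. Nothing closes the window during a long interval between courses or reopens it at the next infusion.

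The same paragraph adds that "most patients will not be considered for further treatment with Ruxience until at least 6 months from the date of last infusion". That is the only statement about the re-treatment interval.

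The CV code list in Annex 1, Table 2 includes deaths: it opens with "Fatal and non-fatal 10000891 Acute myocardial infarction" and has a further block of terms that count only when fatal.

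Malignancy and NMSC follow an ever-exposed rule, so this point does not touch them.

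**The concern.** The 270 days express how long the plan regards a patient as at drug-related risk after an infusion. If the end of the window is tied to the final infusion on record, an interval of more than 270 days between two infusions is counted as exposed in full. The same stretch of time in a patient who is never re-treated is not counted at all. Two patients with identical histories up to day 300 are then handled differently because of what happens afterwards.

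This matters if re-treatment is related to the event or if risk falls during the gap. Event-free patients who go on to another course contribute gap time to the denominator. Patients whose event in the gap ends treatment, and all who die in the gap, contribute neither the event nor the gap time. The study has no comparator, so the absolute rate is the result and an error of this kind cannot cancel in a contrast. Infections are an important identified risk and cardiovascular disease an important potential risk in the risk management plan the protocol cites.

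**Working it through.** **Plan's own figures.** No rate or sample size in the protocol depends on this window, so there is no figure to reproduce. Table 1 was checked in passing: exact 95% intervals for 22/73, 3/73, 1/73 and 0/73 agree with the printed bounds. Also, 270/30.4375 = 8.9 months, consistent with the stated 9.

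**When a gap exists.** A gap needs an interval above 270 days. The stated minimum is 6 × 30.4375 = 183 days, so re-treatment up to 270 − 183 = 87 days after that minimum leaves no gap.

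**The literal rule applied to three patients, each infused on day 0.**
- Event-free, re-treated on day 365, none later: the window ends on day 365 + 270 = 635, and the 365 − 270 = 95 gap days are in the denominator.
- Serious infection on day 300, re-treated on day 365: the event counts, with 300 days of person-time.
- Serious infection on day 300, never re-treated: the window ended on day 270, so the event and the 30 days before it are excluded.

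**Formula.** Let λ be the on-drug rate, T the time within 270 days of an infusion, G the gap time that the literal rule counts, g = G/(T + G), h the rate in the gap relative to λ, and p the probability of re-treatment after an event in the gap. Literal events are approximately λT + hλpG, so

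literal rate / on-drug rate ≈ (T + hpG)/(T + G) = 1 − g(1 − hp).

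The base rate cancels. The ratio is 1 if g = 0, or if h = 1 and p = 1. For fatal events p = 0 necessarily, and the ratio is 1 − g.

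**Simulation, all inputs assumed.** 3,000,000 patients per scenario; on-drug rate 4.1 per 100 person-years (borrowed from 3/73 = 0.041 in Table 1, which is a proportion without person-time); entry uniform over 3 years; 15% stopping per course; one infusion date per course; intervals log-normal with a floor of 180 days; follow-up ended at the first event wherever it fell. Entries are the rate under the literal window divided by the rate under windows of 270 days from each infusion.

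| Median interval | g | h=1, p=1 | h=0.5, p=1 | h=1, p=0.5 | h=0.5, p=0.5 | p=0 |
|---|---|---|---|---|---|---|
| 200 days | 0.1% | 1.000 | 1.000 | 1.000 | 0.999 | 0.999 |
| 270 days | 7% | 1.000 | 0.964 | 0.963 | 0.945 | 0.928 |
| 365 days | 16% | 1.001 | 0.921 | 0.921 | 0.881 | 0.84 |
| 450 days | 21% | 1.002 | 0.895 | 0.896 | 0.841 | 0.79 |

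The formula agrees. At 365 days with g = 0.158: 1 − 0.158 × 0.5 = 0.921; 1 − 0.158 × 0.75 = 0.882; 1 − 0.158 = 0.842. At 450 days with g = 0.212 and p = 0: 0.788.

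The per-infusion window returned 4.10–4.11 per 100 person-years in every scenario, the literal window 3.23–4.11. No scenario showed a material upward bias.

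**The case against.** The strongest reply is that *last infusion* need not mean the final one. Later in the same paragraph, the 6-month minimum before further treatment is counted from the last infusion. There the term must mean the most recent infusion, since more treatment follows. With evaluation tied to being exposed, a rolling window is a fair reading, and on it the dependence on the future disappears. This stands as far as it goes, so the protocol is ambiguous rather than plainly wrong. It does not close the matter: the window still starts only at initiation, so a patient whose window lapsed at day 270 and who is infused at month 12 has no stated way back in.

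Further objections:
- A reader might infer that gaps over 270 days will be common. The protocol does not support that. It gives only a minimum, and that minimum is shorter than 270 days.
- The premise speaks of risk subsiding after discontinuation, not between courses of continuing intermittent therapy. That is fair, and it weakens any claim that gap risk must be lower. It does not help with fatal events, after which re-treatment is impossible.
- A reader might infer that the rule drops events that lead to stopping. An event within 270 days of an infusion counts even if treatment then ends; only later events without a subsequent infusion are lost. The fix below does not recover those either. It removes gap time and gap events together, so that numerator and denominator match.
- The written rule needs one final infusion date per patient, whereas the fix needs all of them. Section 9.4 lists continuation on drug and dates and reasons for stopping, but does not confirm that each infusion date is held. This stands.
- The study is descriptive, and Table 1's interval for 3/73 runs from 0.009 to 0.115, about 13-fold. At similar precision the shift would be small beside sampling error. But Table 1 is not the planned size, and the bias would not shrink with more patients.
- An SAP may settle the handling of gaps. The protocol, however, states the window itself, and that stated rule is what needs correcting.

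**Conclusion.** The point holds conditionally. If the window ends 270 days after the final infusion on record, exposure in long gaps depends on later re-treatment, every fatal gap event is excluded, and the serious infection and CV rates are liable to downward bias. If the most recent infusion is meant, the rule is incomplete because re-entry is undefined. Either way the sentence should be changed.

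The size cannot be derived from the protocol. Under the assumptions above it is about nil when courses nearly always fall within 270 days, and also when gap risk equals on-drug risk and re-treatment is independent of the event. It is roughly 16–21% at assumed median intervals of 365–450 days (about 12–15 months) if events always preclude re-treatment, and 8–10% at the same intervals if gap risk is halved and re-treatment is unaffected. A reader might go further and conclude that the reported rates will be too low. The documents do not support that, because they fix neither the reading of the rule nor the intervals.

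**What to change.** In section 9.7, state that for serious infections and CV events on-drug time is the union of windows from each infusion to the earlier of the next infusion or 270 days. Suspend both person-time and event counting from day 271 until the next infusion, and keep the listed censoring dates. Say also whether an event in a suspended interval ends follow-up for that endpoint, as was assumed in the check above. Report the definition from initiation to final infusion plus 270 days as a sensitivity analysis.

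The cost is a short amendment, record splitting at infusion dates, and somewhat less person-time in the main analysis (0.1% to 21% in the assumed scenarios). Every infusion date is needed. If the register does not hold the intermediate dates, state this as a limitation in section 9.9, with the expected downward direction.

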9.8. Quality Control

BSRBR-RA have guidelines in place to monitor and maintain the quality of the data received. All information received on serious adverse events are reviewed by 1 of 2 trained registered nurses prior to coding. Reports can be sent from hospitals treating the patient, the patients themselves, or the national registers. Reporting malignancies to the national cancer registries is mandatory by law in the UK. To allow serious adverse events to be processed, the following information is required as a minimum:

- A legible and recognised disorder/sign/symptom;
- The date of event;
- Which targeted therapy drug(s) the patient was on at the time of the event.

Where information is missing, the BSRBR-RA pharmacovigilance team contacts the hospital to validate and confirm the details around the serious adverse event. Where a serious adverse event is patient reported, a request for information is sent to the hospital for validation. Events that do not fall under the definition of a serious adverse event are not subject to such validation. The data undergo regular validation checks both manually and automatically.

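### For serious infection and CV events, the 270-day window keeps running after a patient starts another targeted therapy or rituximab product, and the protocol describes no check on this

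*Protocol*

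**What the plan says.** The research question (Protocol section 8) concerns patients who initiate Ruxience, a single product. Section 9.7, under Risk Window, opens with the general rule, in which the first event ends person-time: "Patients will be evaluated for safety events of interest while exposed to Ruxience and accrue person-time from Index Date until the first occurrence". Further stopping reasons, ending with three years followed, are "death, date of last scheduled clinical data provision to the register, lost to follow up, exit from the register or completion of 3 years".

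For outcomes where the section expects "that increased risk subsides after the drug is discontinued (ie, serious infections, CV events"), the general rule is replaced by "a risk window from Ruxience initiation until 270 days (eg, 9 months) after last infusion", justified by the drug's half-life and mechanism. The exceptions follow: "This does not apply to patients who were lost to follow-up, have exited the registry, completed 3 years of follow-up", or a most recent data provision that falls inside the 270 days. In those cases censoring is at that date.

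The only switching analysis mentioned in 9.7 compares new users with patients who came from the originator, and it is to be done only if numbers allow. It concerns entry to Ruxience, not departure from it. Malignancy and NMSC have their own rule, in which a patient once exposed stays at risk.

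In the ENCePP checklist (Annex 2), item 10.8 on sensitivity analyses and item 7.3 on information bias, which covers exposure misclassification, are both marked not applicable. Section 9.9 discusses endpoint misclassification and the lack of a comparator, but not switching away from Ruxience.

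**The concern.** The general rule says "Patients will be evaluated for safety events of interest while exposed to Ruxience", and the result is to be read as a Ruxience rate. Yet a patient who stops Ruxience and starts another biologic, a targeted synthetic DMARD or another rituximab product inside the 270 days goes on contributing events and person-time to Ruxience until the window closes. During that overlap two drugs may be acting, and the rules assign everything to one of them.

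Switching is foreseeable in this setting. Section 7 names two other EU-approved rituximab biosimilars, and section 9.4 expects many patients to arrive from the originator. Section 9.7 also notes that "most patients will not be considered for further treatment with Ruxience until at least 6 months from the date of last infusion". The 270-day tail therefore extends about 3 months past the earliest point at which most patients would be considered for another course.

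At stake is how far the serious infection and CV rates can be attributed to Ruxience. The absolute rate is the whole result. There is no contrast in which a shared distortion could cancel, and the protocol describes no output that would show how large the overlap is.

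**Working it through.** **1. The protocol's own figures.** Table 1 (section 9.5) is the only statistical figure given. Exact (Clopper-Pearson) 95% limits reproduce all six rows to three decimals; for serious infection and for CV events, 3/73 = 0.041 (0.009 to 0.115). The point does not rest on these figures.

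**2. The two stopping lists in section 9.7, side by side.**

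| Reason to stop person-time | General list | Exceptions to the 270-day window |
|---|---|---|
| First event | yes | not repeated |
| Death | yes | not repeated |
| Data provision date | yes (last scheduled) | yes (most recent, if inside the window) |
| Loss to follow-up | yes | yes |
| Exit from the register | yes | yes |
| 3 years of follow-up | yes | yes |
| Start of another targeted therapy | no | no |
| Start of another rituximab product | no | no |

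Even read together, the lists give no stop at a switch. I take the last infusion to mean the last Ruxience infusion, because the window is justified by that drug's half-life.

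**3. Overlap for one patient.** Taking 6 months as 183 days, a patient who starts another drug at that point spends 270 - 183 = 87 days of the tail on it, and 87/270 = 32%.

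**4. Share of person-time affected.** The protocol gives no switch rate, switch timing or mean on-drug time. The inputs here are assumptions: proportion switching s = 10-30%, months from last infusion to switch m = 2-6, mean on-drug time 1.5 person-years. With the window taken as 9 months,

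f = s × (9 - m)/12 ÷ 1.5

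| s | m | f |
|---|---|---|
| 10% | 6 | 0.10 × 3/12 ÷ 1.5 = 1.7% |
| 10% | 2 | 0.10 × 7/12 ÷ 1.5 = 3.9% |
| 30% | 6 | 0.30 × 3/12 ÷ 1.5 = 5.0% |
| 30% | 2 | 0.30 × 7/12 ÷ 1.5 = 11.7% |

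**5. Effect on the reported rate.** Let RR be the event rate after the switch divided by the rate in the rest of the window. Then

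reported rate ÷ rate without the overlap = 1 + f × (RR - 1)

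| RR (assumed) | f = 1.7% | f = 11.7% |
|---|---|---|
| 0 | 0.983 | 0.883 |
| 0.5 | 0.992 | 0.942 |
| 1 | 1.000 | 1.000 |
| 2 | 1.017 | 1.117 |

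The shift is at most f in either direction for RR between 0 and 2, and its sign depends only on whether RR is above or below 1.

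**6. Wider assumptions.** Suppose 10-40% of patients switch at day 90 or 183, with a mean window of 270 to 635 days. The lowest share is 0.10 × 87/635 = 0.014 and the highest is 0.40 × 180/270 = 0.267. With RR from 0.5 to 2, the ratio in step 5 is 0.99 to 1.01 at the low end and 0.87 to 1.27 at the high end.

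**The case against.** The case for leaving the protocol alone has four parts.

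- **The tail is the exposure definition.** For these outcomes, section 9.7 treats a patient as exposed until 270 days after the last infusion, for pharmacological reasons. On that definition a patient who starts another drug in the window is still exposed to Ruxience, and censoring at the switch could discard events that B-cell depletion caused. This stands. A reader might infer that the 270-day rule is wrong, or that overlap events belong to the next drug. The documents support neither reading: such an event may be due to either drug.
- **The size is assumed.** This also stands. A reader might infer that Ruxience rates will be overstated, but nothing in the protocol says whether the rate on the next drug is higher or lower. The upper figure of 11.7% needs 30% of all patients to switch at 2 months. At 6 months the same formula gives 1.7-5.0%.
- **Random error may be larger.** In Table 1 the limits for 3/73 run from about 78% below the estimate (0.009/0.041 = 0.22) to about 180% above it (0.115/0.041 = 2.80). By a simple Poisson approximation, a 95% margin of 12% needs (1.96/0.12)² ≈ 267 events, and one of 5% needs (1.96/0.05)² ≈ 1,537. This limits the importance of the point. It does not remove it, because a wide interval does not tell the reader which events occurred after a switch.
- **A sensitivity analysis belongs in the SAP.** Section 9.7 refers to a SAP, which is not shown and may contain such a check. It would be wrong to conclude that none exists. The stopping rules, however, are fixed in the protocol itself as lists, and applied as written they carry follow-up through a switch.

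**Conclusion.** The point holds for serious infections and CV events. Both stopping lists in section 9.7 omit the start of another targeted therapy or rituximab product, so all events and person-time in the overlap are attributed to Ruxience, in a study with a product-specific question and no comparator.

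Neither size nor direction can be determined from the protocol. The illustrative 2-12% of person-time, and a rate shift of up to that share either way, rest entirely on the assumed switch proportion, timing, mean on-drug time and rate ratio. The overlap is limited to the 270-day tail.

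The point does not extend to malignancy or NMSC, where following patients through later drugs is deliberate. It is a worthwhile improvement in attribution, not a fault that invalidates the main analysis.

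**What to change.** In section 9.7:

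1. Keep the window to 270 days after the last Ruxience infusion as the main analysis for serious infections and CV events.
2. Add one sensitivity analysis for these two outcomes in which follow-up also ends at the first dose of any other biologic, targeted synthetic DMARD or rituximab product.
3. Report main-analysis events and person-time before and after such a switch, with the events broken down by the targeted therapy recorded at the event.

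The inputs appear to be available. Section 9.4 has the register updating anti-rheumatic treatment at each follow-up, with stop dates and reasons. Section 9.8 makes "Which targeted therapy drug(s) the patient was on at the time of the event" part of the minimum information for processing a serious adverse event.

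The cost is one extra analysis and one table. The sensitivity analysis will have fewer person-years and may lose some genuine carry-over events, which is why it should stand beside the main analysis and not replace it.

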9.4. Data Sources

BSRBR is the source of core baseline data, including patient demographics and disease characteristics collected by the recruiting clinician, using a standardised form.

Follow up

BSRBR data are the source of information on anti-rheumatic treatment, updated every 6-12 months depending on how long a patient has been in the register (6 monthly for the first 3 years and 12 monthly thereafter). This change is to reduce the burden of data capture on study sites, but the same data are collected at each follow-up. As many patients starting Ruxience will have been enrolled previously when they started Mabthera, follow-up may only be every 12 months. Some patients starting Ruxience as their first anti-B cell therapy will provide data more often as per the BSRBR protocol and some trusts may decide themselves to reconsent patients each time they switch drugs and send data every 6 months for 3 years again. Data captured includes continuation on drug and dates and reasons for stopping, with details of any change in dose and commencement of any new co therapy. Clinical information to permit calculation of the Disease Activity Score in 28 joints (DAS-28) is also collected.

Endpoints

BSRBR data include reports of serious morbidity reported directly by the rheumatology team at each scheduled follow-up date. For serious events additional data are captured, either against a pre-specified set of questions for certain events of special interest or using an open request for additional data. All events included in this protocol are considered events of special interest. All serious morbidities reported to BSRBR are coded by a trained nurse using the Medical Dictionary for Regulatory Activities (MedDRA).

BSRBR is linked to the UK national death and cancer registers which allow the “flagging” of individuals such that if they die or are entered in a cancer register, the BSRBR-RA learns of the event and obtains death certificate details or cancer register details. These data are held in a separate secure data safe haven at the University of Manchester. On average deaths are usually reported within 1 week to the national register although cancers can take much longer due to the structure of national reporting. BSRBR-RA received a download of death and cancer on average once/year.

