12. PLANS FOR DISSEMINATING AND COMMUNICATING STUDY RESULTS

In the event of any prohibition or restriction imposed (eg, clinical hold) by an applicable competent authority in any area of the world, or if the investigator party responsible for collecting data from the participant is aware of any new information which might influence the evaluation of the benefits and risks of a Pfizer product, Pfizer should be informed immediately.

Annual reports will be prepared by BSRBR and shared with Pfizer. Analysis using linked register data through 3 years of follow up will be the basis for the study final report. Data may be used in regulatory communications external to the UK or for contextualisation purposes. Manuscripts based on specific endpoints of interest may be developed for publication purposes.

In the event of any prohibition or restriction imposed (eg, clinical hold) by an applicable Competent Authority in any area of the world, or if the investigator is aware of any new information which might influence the evaluation of the benefits and risks of a Pfizer product, Pfizer should be informed immediately.

In addition, the investigator will inform Pfizer immediately of any urgent safety measures taken by the investigator to protect the study patients against any immediate hazard, and of any serious breaches of this NI study protocol of which the investigator becomes aware.

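### As written, the CV risk window in Protocol 9.7 does not count an in-window CV death unless a clinical form follows it, although the draft CV definition includes fatal events

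*Protocol*

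**What the plan says.** Two rules in Protocol 9.7 (Risk Window) decide when a patient stops contributing to the CV rate.

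- **General rule.** Person-time runs "until the first occurrence of the event of interest, death, date of last scheduled clinical data provision to the register", or to loss to follow-up, register exit or 3 years. Death is a separate stop, and the form date is the last *scheduled* one.
- **Rule for serious infections and CV events.** These use a "risk window from Ruxience initiation until 270 days (eg, 9 months) after last infusion". An exception covers several groups, including patients "for whom the most recent date of clinical data provision to the register is within the 270 day window"; they are censored on that date. Here the form date is the *most recent* one, and death is not mentioned.

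Protocol 9.4 gives the form schedule as "6 monthly for the first 3 years and 12 monthly thereafter" and expects that many Ruxience starters may be on the yearly schedule. The same section describes linkage to the national death register with certificate details: "On average deaths are usually reported within 1 week to the national register". The register receives a download about once a year.

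Annex 1 Table 2 makes fatal events part of the CV definition. One list opens with "Fatal and non-fatal 10000891 Acute myocardial infarction", and a second, long list holds codes that count only when fatal. Protocol 12 adds: "Analysis using linked register data through 3 years of follow up will be the basis for the study final report". It does not name deaths specifically.

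**The concern.** A patient with a non-fatal CV event normally lives to a later form that covers it. A patient who dies may have no later form. The death is still known, because it reaches the register through linkage, but the form rule has already stopped that patient's follow-up. Censoring then depends on the outcome, and the events lost are the most severe ones. Codes that count only when fatal are the most exposed. Malignancies do not share the problem, because 9.7 does not cut their follow-up at the last form. Protocol 9.9 does not mention this loss and regards missed serious events as unlikely.

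**Working it through.** **Inputs from the Protocol.** Window end: 270 days after last infusion (9.7). Form interval: 6 or 12 months (9.4). Table 1 (9.5): 3 CV events in 73 patients, 0.041 (95% CI 0.009 to 0.115).

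**Assumptions, not in the Protocol.** Fatal share of first CV events, f = 10% to 40%. Share of deaths followed by a clinical form dated after death, q = 0, 0.5 or 1.

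**Step 1: the plan's own figure.** An exact (Clopper-Pearson) interval for 3/73 gives 0.041 (0.009 to 0.115), as printed. Nothing in Table 1 is disputed. It has no fatal/non-fatal split, so it cannot size this problem.

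**Step 2: order of dates.** Let L be the last infusion, F the last form before death and D the death.

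- The death is in the window if D ≤ L + 270 days.
- F < D, so F < L + 270 days: the form also lies inside the window.
- If no form follows D, F is the most recent data provision. The exception applies and follow-up ends at F, before D.

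Illustration: infusion on day 0, form on day 90, fatal myocardial infarction on day 180. The window would close on day 270, but the patient is censored on day 90. The result does not depend on the form interval. The general rule does not rescue the event if its stops are read as earliest-first, because F still precedes D.

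**Step 3: share of CV events lost.** Lost share = f × (1 − q).

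| f | q = 0 | q = 0.5 | q = 1 |
|---|---|---|---|
| 10% | 10% | 5% | 0% |
| 20% | 20% | 10% | 0% |
| 30% | 30% | 15% | 0% |
| 40% | 40% | 20% | 0% |

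**Step 4: effect on the rate.** The rule also removes person-time, so it was simulated with 400,000 patients per scenario. Further assumptions: 4.1 CV events per 100 person-years (0.041 from Table 1, borrowed as an annual rate); other-cause death 1 per 100 person-years; re-treatment every 0.6 years with probability 0.7; uniform entry over 2.5 years; end at 3 years. Ratio of the rate under the written rule to the true rate, 6-month / 12-month forms:

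| f | q = 0 | q = 0.5 | q = 1 |
|---|---|---|---|
| 10% | 0.89 / 0.90 | 0.95 / 0.96 | 1.01 / 1.03 |
| 20% | 0.79 / 0.80 | 0.91 / 0.93 | 1.03 / 1.06 |
| 30% | 0.70 / 0.70 | 0.87 / 0.89 | 1.03 / 1.08 |
| 40% | 0.60 / 0.60 | 0.83 / 0.85 | 1.05 / 1.12 |

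With q = 0, none of the in-window fatal first events is kept, and the rate falls from about 4.1 to about 3.7, 3.3, 2.9 and 2.5 per 100 person-years. With q = 1 all are kept, but the ratio is slightly above 1: deaths are counted to their own date while survivors' time still stops at their last form. A repair has to avoid that opposite error too.

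**The case against.** The strongest reply is that nothing in the Protocol says forms stop after a death. Hospital staff enter the data (9.6). Reports may come from hospitals, patients or national registers, and the pharmacovigilance team contacts the hospital when information is missing (9.8). A report dated after the death could move the censoring date past it. The general rule also lists death as a separate stop, which would have little purpose if follow-up always ended at an earlier form, so counting to death may have been intended. This stands in part. It means that the loss may be small or nil. It does not remove the defect, because no section says that a later report or a linkage record resets the censoring date, and the two rules in 9.7 differ.

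A second reply is that deriving a censoring date belongs in the SAP. Here, though, the Protocol states the rule itself, and an SAP that follows it inherits the loss.

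A reader might extend the point to serious infections, since the same window applies. The documents do not support a separate fatal rate there. Protocol 9.3.2 specifies hospitalised infections, and Table 2 requires hospitalisation and/or parenteral antibiotics. Neither has a fatal-only component, so a death certificate alone does not show that the definition was met.

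A reader might also infer that the CV rate will be 20-40% too low. That needs both a fatal share of that size and no form after any death, and the documents give neither. Table 2 is moreover a draft code list, and the cardiac endpoint in 9.3.2 is broader, which could lower the fatal share.

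**Conclusion.** The point holds for CV events. Under the written rule, an in-window CV death with no later clinical form is not counted, although the draft definition includes it and the register learns of it. To the extent that deaths lack a later form, the fatal part of the CV rate is biased low.

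The size cannot be derived from the documents. For an assumed fatal share of 10-40%, the loss of CV events runs from 0% (every death followed by a form) through 5-20% (half) to 10-40% (none). It would be wrong to say that fatal events are always lost, or to quote one percentage. The change is worth making because the data needed are already received; confidence in the practical impact is moderate.

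**What to change.** In Protocol 9.7:

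1. Reconcile the two stopping rules: state whether the last scheduled or the most recent data provision governs, and how death ranks against it.
2. For the fatal CV component, end follow-up for every patient, dead or alive, at the earliest of the end of the 270-day window, death, 3 years, register exit and the date to which death linkage is complete. Do not end it at the last clinical form.
3. Report this fatal CV rate beside the form-based non-fatal CV rate, and define the overall CV rate as the sum of the two. Since 9.7 counts first events, a patient with an earlier counted non-fatal CV event should not be counted again in the sum.

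A single sentence saying that in-window deaths count at the date of death would be simpler. It would add deaths without the matching survivor time, which is the pattern behind the ratios of 1.01 to 1.12 above. Using the linkage date for everyone keeps numerator and denominator on the same basis.

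The cost is a short edit, one extra rate and no new data collection. The two components have slightly different person-time. Because downloads come about once a year, the linkage cut-off may fall some months before the end of data collection.
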